#### **Analysis plan**

#### **Primary Analysis**

The main outcome of the trial (preliminarily GHQ-12 scores) will be assessed through a linear regression model, specified as:

$$Y_{it} = \alpha + \beta_1 S_i + \beta_2 Y_{it-1} + \beta_3 X_i + \epsilon_{it}$$

#### Where:

- $Y_{it}$  is the level of an outcome measure observed by participant I at time t (the T2 survey).
- α is a regression constant.
- $S_i$  is a binary indicator of treatment assignment, set to 1 if participants have been assigned to treatment, and 0 else.
- $Y_{it-1}$  is participant I's baseline score for the outcome measure.
- $X_i$  is a vector of participant level characteristics (gender, age, ethnicity, phase 1 or phase 2).
- $\epsilon_i$  is a Huber white robust standard error.

Where participants have T2 data but not T1 data,  $Y_{it-1}$  will be inputted as 0, and a binary variable contained within the vector X denoting that baseline data are missing will be set to 1 (else 0).

Secondary analysis will be considered using matched exclusion. For this analysis the model used will be identical to the main model, with the data used for the model having been subject to exclusion. Participants for exclusion will be matched on characteristics contained within X and on their baseline GHQ-12 data.

The sample size for the RCT was based on a one-sided hypothesis and this will be reflected in the reporting of the results of the primary analysis.

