As set out in the previous protocol, we initially planned to work with six local authorities in total, with all of them providing Schwartz Rounds face-to-face. We expanded the study to include five additional local authorities in order to increase the sample size and the chances of avoiding a false negative result (i.e., failing to identify a positive effect on staff levels of stress caused by Schwartz Rounds). The original six authorities are referred to as phase one (of the trial), and the additional five authorities as phase two (of the trial). The plan at the outset, at the point when the five new authorities were recruited, was that they would also provide face-to-face Schwartz Rounds for their staff, in the same way the authorities in phase one had done. However, due to the Covid-19 pandemic and associated lockdowns and social distancing requirements this was not possible. Therefore, the phase two authorities will deliver virtual Schwartz Rounds (also called Team Time) instead.

Although there are no published studies that we could find which compare the effectiveness of face-to-face Schwartz Rounds with virtual Schwartz Rounds, there are studies of face-to-face counselling compared to online counselling, which tend to find similar levels of effectiveness (e.g., Barak et al, 2008; Stefanopoulou et al., 2018). This could suggest that virtual Schwartz Rounds may have a similar effect to that of face-to-face Schwartz Rounds (albeit we intend to consider this empirically as part of our exploratory analysis).

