# Design

The overall study design is an individually randomised control trial with group delivery of the intervention. It is a two-arm study, with an intention-to-treat intervention group and a waiting-list control, with the aim of assessing the effectiveness of Schwartz Rounds within children's social care in relation to the psychological well-being of staff.

Trial Type and Number of Arms		Randomised control trial with two arms (intention-to-treat and waiting-list control)	
Unit of Randomisation		Individual members of staff	
Stratification Variables (if applicable)		Phase (one or two)	
Primary Outcome	Variable	Psychological well-being of staff	
	Measure (instrument, scale)	GHQ-12	
Secondary Outcome(s)	Variable(s)	Sickness-related absence	
	Measure(s) (instrument, scale)	Self-report	

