#### Randomisation

A researcher not otherwise involved in the study will use staff lists provided by the LAs to create equal-sized intervention and waiting-list-control groups, with staff randomly allocated to each group.

To achieve this, each LA will provide a pseudonymised list of staff working in children's services (e.g., based on employee numbers). Using Excel's randomisation feature a random number will be generated for each employee, the list will then be sorted from smallest to largest, and then split in half at the median value to create two equal sized groups (plus or minus one, if the list contains an odd number of staff; Zelen, 1979). Each LA will then be given a list of staff in each group, which they can re-identify and circulate, so as to ensure that members of staff know which group they are in (this information will not be shared with staff until after the T1 survey has been closed).

The control group will be asked not to attend Schwartz Rounds during the trial period but will continue to receive 'business as usual' support from their authorities. The intervention group will also continue to receive 'business as usual' support but will also be invited to attend Schwartz Rounds (whether virtually or face-to-face). For social workers, 'business as usual' support will likely include monthly one-to-one supervision with a line manager. In some sites, this may also include group supervision, reflective practice groups or other group-based interventions. Some sites may also provide staff with counselling services where this is required. For non-social work staff, 'business as usual' support may include some or none of these elements. We will ask staff about what other support they have available and what other support they have accessed as part of the T2 survey.

Direct contamination (by members of the control group attending Schwartz Rounds) will be measured via sessional feedback questionnaires. The extent and significance of indirect contamination (by members of the intervention group talking about the intervention outside of rounds) will be explored via focus groups at T2.

Analysts will be blinded to group allocation in relation to GHQ-12 and group-level absence data.

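### Staff are randomised separately within each of 11 local authorities, but the design table names only phase as stratifier and the treatment-effect models adjust for phase, not authority

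*Protocol*

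**What the plan says.** **How staff are allocated (Protocol, Randomisation).** The unit of listing is the authority: "each LA will provide a pseudonymised list of staff working in children's services". A random number is attached to each employee, and "the list will then be sorted from smallest to largest, and then split in half at the median value to create two equal sized groups", with a tolerance of one for an odd-length list. The result goes back authority by authority: "Each LA will then be given a list of staff in each group".

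**How many authorities (Protocol, Background and Problem Statement).** "The original six authorities are referred to as phase one (of the trial), and the additional five authorities as phase two (of the trial"). That makes 11.

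**What the design table records (Protocol, Design).** The only stratification variable given is "Phase (one or two").

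**What the models adjust for (Protocol, Analysis plan).** The primary regression contains treatment, the baseline score and X, which "is a vector of participant level characteristics (gender, age, ethnicity, phase 1 or phase 2"). Secondary analyses a (caseness) and b (sickness absence) reuse this model with the outcome replaced. Both 2SLS stages of analysis c carry a vector X of participant characteristics, not listed again and read here as the same one. Local authority is named only under Exploratory Analysis, among several variables to be examined for association with GHQ-12 scores.

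**The concern.** The design table and the allocation procedure disagree on what the strata are. Phase is a coarser grouping of authorities: splitting within authorities balances phase automatically, but a phase term does not represent the 11 strata. The models take over the table's version, so the treatment effect is not estimated within the groups in which staff were randomised.

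Two things are at stake. The first is precision, since variance between authorities that the design has balanced stays in the residual. The second is protection against an uneven authority mix. Balance within authority holds for the randomised lists, but the analysed set is the T2 responders. The protocol gives reasons why response may depend on authority: the authorities send the reminders, one opted out of the prize draw, and each runs its own communication strategy. Staff know their arm once the T1 survey has closed. If one arm responds better in some authorities and worse in others of the same phase, stress differences between authorities enter the treatment estimate, and the phase term cannot take them out.

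**Working it through.** **Inputs from the protocol (Sample Size Calculations).** MDES 0.23 SD; one-sided alpha 0.05; power 0.8; baseline/endline correlation 0.33; 238 per arm, 476 in total; loss scenarios of 50% and 75%.

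**Inputs assumed.** The protocol gives no authority-level ICC and no response rates by arm and authority. ICC is taken from 0 to 0.10; the response patterns are stated below.

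**1. The plan's own figure.** n per arm = 2(1.645 + 0.842)² / 0.23² = 234, within 3% of 238. At 238 per arm the MDES is 0.228 and power is 80.6%. This match does not use the 0.33 correlation; with residual variance 1 − 0.33² the formula gives 209. Dropout: 238/0.5 = 476 and 238/0.25 = 952 per arm, as stated.

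**2. Precision, with balance within authority kept.** Ignoring baseline and phase, adding authority scales the SE by √(1 − ICC): 0.990 at ICC 0.02 and 0.975 at 0.05. The planned model already holds baseline and phase, so the real gain is smaller. A simulation used 476 responders in 11 authorities (6 and 5), 1:1 within authority, within-authority correlation 0.33, robust SEs and 6,000 runs per setting. It compared the model with baseline and phase against the model with baseline and authority indicators:

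| ICC (assumed) | Mean SE, phase | Mean SE, authority | Power at 0.23, phase | Power at 0.23, authority | One-sided type I error, phase |
|---|---|---|---|---|---|
| 0 | 0.0866 | 0.0866 | 84.6% | 84.7% | 4.8% |
| 0.02 | 0.0861 | 0.0857 | 85.0% | 85.2% | 5.0% |
| 0.05 | 0.0853 | 0.0844 | 85.0% | 85.3% | 4.75% |
| 0.10 | 0.0838 | 0.0821 | 86.6% | 87.3% | 4.5% |

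**3. Response imbalance not aligned with authority stress.** The treated share of responders was drawn between 30% and 70% for each authority, independently of its stress level. One-sided type I error for ICC 0.02, 0.05 and 0.10 was 5.3%, 5.5% and 5.6% with phase only, against 5.0%, 5.2% and 5.2% with authority indicators. The Monte Carlo standard error near 5% is √(0.05 × 0.95 / 6000) = 0.28 points, so even the largest excess is only about two standard errors.

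**4. Response imbalance fully aligned with stress (assumed worst case).** Suppose half the staff are in authorities that sit 0.3 SD higher, that T2 response there is 35% (intervention) against 25% (control), that the rates are reversed elsewhere, and that the contrast lies within phases. A 0.3 SD split between equal halves has variance 0.15² = 0.0225, an authority share of about 2%.

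- Share of responders from the higher-stress authorities: 0.35/0.60 = 0.583 (intervention) and 0.25/0.60 = 0.417 (control).
- Bias without baseline adjustment: (0.583 − 0.417) × 0.3 = 0.05 SD; 0.05/0.23 = 22% of the MDES.
- Bias after baseline adjustment, if the same gap is present at T1 and the slope is 0.33: 0.05 × (1 − 0.33) = 0.0335, about 0.034 SD; 0.0335/0.23 = 15%.
- Responders without T1 data have baseline set to 0 with a flag, so nothing is absorbed for them. The figure therefore lies between 0.034 and 0.05 SD, depending on how many they are.
- With SE 0.0861, a shift of 0.0335 in the favourable direction is 0.39 SE. One-sided type I error becomes 1 − Φ(1.645 − 0.39), about 10%. In the other direction it costs power instead.

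**5. Cost in degrees of freedom.** Eleven authorities need 10 indicators, and these replace the single phase indicator: 10 − 1 = 9 more, out of about 476 observations.

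**The case against.** The strongest reply is that omitting strata does not invalidate a randomised comparison. While balance holds, the test is slightly conservative, the sample size does not move and the gain in power is close to nothing. All of that stands.

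It is also fair to say that the worst case in step 4 is contrived. It needs arm differences in response that reverse between authorities and line up exactly with which authorities are more stressed. Nothing in the protocol shows either, and without the alignment the effect is marginal (step 3). That stands too, and it is why the 15% is a ceiling under stated assumptions and not an expected bias.

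Three stronger inferences are not supported:

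- A reader might infer that authority is ignored altogether. It is not: Exploratory Analysis examines it against GHQ-12 scores. That is not adjustment of the treatment effect, so the omission concerns the primary and secondary treatment-effect models.
- A reader might take the 22% of the MDES as the bias of the planned analysis. It belongs to an estimate without the baseline score, whereas the planned model includes it. Phase would also remove any part of the gap that lies between phases.
- A reader might treat 50% to 75% loss as expected. The sample size table gives these as planning scenarios.

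The Randomisation section does not use the word stratified. But one list per authority, a median split with an odd-length rule, and groups returned to each authority leave no other natural reading.

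**Conclusion.** The inconsistency is established from the protocol alone: allocation is 1:1 within each of 11 authorities, the design table says phase, and the primary and secondary treatment-effect models carry phase without authority.

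Its consequence is small in the likely case and moderate at worst. For an assumed ICC up to 0.05 the power change is 0.3 points or less, and 0.7 points at 0.10. A material bias needs differential response aligned with authority stress levels. Under the assumptions of step 4 it is about 0.034 SD, 15% of the MDES, after baseline adjustment. The ICC, the 0.3 SD gap and the response rates are assumptions, not figures from the protocol. This is a point that should be fixed because the remedy is cheap and matches the design. The documents do not support reading it as a flaw that overturns the primary test, its alpha or its power.

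**What to change.** 1. In the Design table, give the stratification variable as local authority (11 strata, nested in phase).
2. In X, replace the phase indicator with indicators for the 11 authorities. Phase is nested and drops out. Apply this to the primary model, secondary analyses a and b, and both 2SLS stages.
3. Record the change as a dated amendment before any unblinded analysis. The protocol is registered, and its Timeline section says that phase one data collection is complete, so a change to the primary model needs a visible date and reason. Phase two T2 collection was still to come at this version, and the protocol plans for analysts to be blinded to allocation for GHQ-12, so this is feasible.

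The cost is about 9 degrees of freedom and one amendment. No new data are needed: responses are collected by site and merged, and authority is already an exploratory variable.

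Authority indicators do not deal with differential non-response within an authority, which remains a separate threat.

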#### **Secondary Analysis**

The main secondary hypotheses are:

- a. The proportion of GHQ-12 scores above the 'caseness' threshold (of 3) at T2 will be lower in the intervention group compared to the control group. We will get evidence for this hypothesis by replacing the outcome measure in the primary analysis above with 'caseness' status (yes or no).
- b. The number of days of sickness-related absence in the intervention group will be lower at T2 in the intervention group compared to the control group. We will get evidence for this hypothesis by replacing the primary outcome measure with the number of days of sickness-related absence and a baseline measure.

c. More regular attendance at Schwartz Rounds will be associated with lower GHQ-12 scores compared with less regular and non-attendance. We will conduct a complier average causal effect (CACE) analysis, with the treatment being replaced by the fraction of sessions attended and the treatment status being used as an instrument.

This will fit using two-stage least squares (2SLS),

```
Attendancei = \alpha + \beta_1 S_i + \beta_2 Y_{it-1} + \beta_3 X_i + \epsilon_i

Y_{it} = delta + \beta_1 Predicted attendance_i + \beta_2 Y_{it-1} + \beta_3 X_i + tau_{it}
```

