#### where:

- Attendance is the fraction of sessions attended.
- $\alpha$  and delta are regression constants.
- $S_i$  is a binary indicator of treatment assignment, set to 1 if participants have been assigned to treatment, and 0 else. This is our instrumental variable.
- Predicted attendance is the fitted value of attendance from the first stage regression.
- $Y_{it-1}$  is participant I's baseline score for the outcome measure.
- $X_i$  is a vector of participant level characteristics.
- $\epsilon_i$  is a Huber white robust standard error.
- *tau*it is a Huber white robust standard error.
- d. Schwartz Rounds will be considered acceptable by the intervention group. We will measure this with the IPE as set out below.

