# **Implementation and Process Evaluation**

The implementation and process evaluation will seek to address the following questions:

- Is it feasible to implement Schwartz Rounds (face-to-face and online) in children's services?
- What adaptations, if any, are made to the intervention as it is implemented in children's services?
- How do social workers and other members of staff view the experience of attending Schwartz Rounds?
- For members of staff in the intervention group who do not attend, what reasons do they give for their non-attendance?
- For members of staff who attend irregularly (between 1-3 Schwartz Rounds), what reasons do they give for their irregular attendance?
- For members of staff who attend regularly (4+ Schwartz Rounds), what reasons do they give for their regular attendance?
- How do key informants within children's services (e.g., Assistant Directors, Principal Social Workers, Heads of Service, facilitators and Practice Leads) view the intervention?
- What impact do attendees think Schwartz Rounds have had on their psychological wellbeing?
- What impact do attendees think Schwartz Rounds have had on their work with children and families?

The primary methods for addressing these research questions will be interviews (with key informants) and focus groups (with members of staff). The data gathered from these methods will be supplemented via sessional feedback questionnaires, completed by participants at the end of each Schwartz Round.

The level of fidelity in each local authority will be assessed jointly by the evaluation and the intervention team, based on Maben et al.'s (2018) nine CMOs. Experienced trainers from the Point of Care Foundation will observe at least one round or virtual round in each site. Researchers from the evaluation team will do the same. The researchers and the experienced trainers will discuss their observations of each site and agree whether they have successfully implemented the intervention.

During both phases of the project, at least two Schwartz Rounds will be observed at each site, one by the Point of Care Foundation and one by a researcher from the evaluation team. Research observations will be recorded in hand-written notes, with reference to the nine CMOs identified by Maben et al. (2018).

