Sessional feedback questionnaires will be handed out on paper to every attendee at a face-to-face Schwartz Round and distributed via Qualtrics to each attendee at a virtual Schwartz Round. These forms are used widely in Schwartz Round studies and ask people to report their subjective experience of having attended. We will also use these as a record of attendance, by asking participants to include their initials and day and month of birth. We will also ask each LA for a record of how many people attended each session. The paper forms will be collected back in at the end of each round and collected from each site by a member of the research evaluation team. The data from the forms (both paper and online) will be entered into SPSS. The SPSS database will be stored securely on a Cardiff University computer. Paper copies are kept in a secure locked cupboard at Cardiff University, accessible only to members of the evaluation team.

Focus groups and interviews will be held for each site, either in the local authority offices or online. Interviews and focus groups will be conducted and facilitated by members of the evaluation team. They will be audio recorded using digital Dictaphones. Recordings will be uploaded to a secure Cardiff computer and deleted from the Dictaphone as soon as reasonably possible. Interviews and

focus group recordings will then be transcribed and analysed using Nvivo, based on a coding framework developed from the relevant research questions.

To help compare the experience of attending and providing face-to-face and virtual rounds, we will also conduct interviews with key informants and staff members in two phase one authorities (who provided face-to-face rounds previously and during the Covid-19 associated lockdown have switched to virtual rounds).

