#### **Cost Evaluation**

An economic evaluation will be incorporated into the trial design for the collection of both costs and outcomes data at T1 and T2. A cost-effectiveness analysis (CEA) will be carried out from a social care perspective.

Costs related to the delivery of Schwartz Rounds will encompass the costs of setting-up and delivering the Schwartz Rounds intervention. These will include training costs for the Practice Lead and facilitators of the Schwartz Rounds at each local authority, venue and catering costs for each face-to-face Schwartz Round and staff costs including time spent attending a Schwartz Round as well as time spent on preparation and administrative tasks in-between each round.

Direct and indirect costs of the intervention will be gathered from each local authority:

- The direct cost of the contract with the Point of Care Foundation is £5,000 per authority.
- Data on room use and catering costs will be collected from each local authority conducting face-to-face Schwartz Rounds.
- Staff time for attendance will be calculated based on sessional feedback questionnaires.
- Staff time for preparation and administration will be collected from each local authority, via interviews with facilitators, Practice Leads and administrators.
- We will also consider what different costs might be associated with virtual rounds, compared to face-to-face rounds e.g., no money required for food, additional costs for IT equipment.

In addition, sickness-related absences will be tracked at the level of the individual social worker to calculate any potential savings resulting from the intervention. This will be based on knowledge of the grade of each social worker randomised in the trial applied to administrative data on sickness-related absence and retention collected from each local authority. This data will be used to calculate any potential savings resulting from the intervention.

The results of the CEA will be expressed in an incremental cost per unit reduction in the GHQ-12 score. The impact of uncertainty on the CEA results will be quantified by carrying out a probabilistic sensitivity analysis and summarising the results using cost-effectiveness acceptability curves.

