#### **Data Protection**

We will only collect and process data in order to address our research questions. In all circumstances, the identities of individuals taking part in the study and the data they provide will be kept confidential and will only be used for research purposes. Participants will be informed of their right not to take part in the study, either by not attending Schwartz Rounds or by attending without taking part in data collection activities.

Data will be processed only when the data subject has given consent to the processing of his or her personal data for the specific purpose of conducting this trial.

All data collected will be stored securely on Cardiff University computers.

Cardiff University's research data protection notice can be read – here.

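### The CACE planned for secondary hypothesis (c) is a rescaling of the primary result and cannot compare regular with less regular attendance; its size also depends on how completely optional forms record attendance.

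*Protocol*

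**What the plan says.** Under Secondary Analysis, hypothesis (c) reads "More regular attendance at Schwartz Rounds will be associated with lower GHQ-12 scores compared with less regular and non-attendance". The list of secondary hypotheses near the start of Impact Evaluation makes the same contrast. The Implementation and Process Evaluation section fixes the groups: one of its questions begins "For members of staff who attend irregularly (between 1-3 Schwartz Rounds", and the next defines regular attendance as four or more. The intervention section gives the reason for four, citing an earlier health-care study that used it as its threshold.

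The analysis for (c) is a CACE, "with the treatment being replaced by the fraction of sessions attended and the treatment status being used as an instrument". The definitions below the equations add that "Attendance is the fraction of sessions attended". Both stages carry the baseline score and the vector X, as the primary model does.

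On measurement, the process evaluation section says of the sessional feedback questionnaires: "We will also use these as a record of attendance, by asking participants to include their initials and day and month of birth". A second source is a count only: "We will also ask each LA for a record of how many people attended each session". The Data Protection section lets staff decline "either by not attending Schwartz Rounds or by attending without taking part in data collection activities". Under Cost Evaluation, "Staff time for attendance will be calculated based on sessional feedback questionnaires".

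**The concern.** The hypothesis compares levels of attendance; the model estimates one slope from one randomised contrast. A single binary instrument identifies a single coefficient, so whatever the result says about regular versus irregular attendance comes from the assumed straight line and not from data. If (c) is reported beside the primary result as evidence that regularity matters, one finding is counted twice. The same number could appear even if only irregular attendance helped, which is the opposite of (c).

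A second, conditional concern is the size of the estimate. The arm difference in recorded attendance is its denominator. If some attendance is never recorded, or cannot be linked to a survey response, and is then treated as zero, the denominator shrinks and the estimate grows. Unreturned forms would also lower the staff-time cost.

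**Working it through.** **The plan's own figure.** The protocol gives no figure for the CACE. Its sample size reproduces: 2 × (1.645 + 0.842)² / 0.23² ≈ 234 per arm, one-sided at 0.05 with 80% power. The stated 238 gives a detectable effect of 0.228, which rounds to the stated 0.23. I use 476 people and an ITT effect of -0.23 SD below.

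**Step 1: what the model estimates.** With one instrument, one exposure, and the same covariates and sample in both stages,

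CACE = ITT coefficient / arm difference in attendance fraction.

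I read X in the attendance model as the X listed for the primary analysis. In 6,000 simulated trials the two sides differed by at most about 1e-14.

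**Step 2: can it see regularity?** Assumptions, since the protocol gives no attendance distribution: in the intervention arm 55% attend none, 30% attend 1-3 rounds (mean 2) and 15% attend 4-6 (mean 5), of six offered; no control attendance; baseline correlation 0.33 as in the sample size table. The expected first stage is (0.30 × 2 + 0.15 × 5) / 6 = 0.225.

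The trial supplies one equation for two unknown group effects: 0.30 × d(1-3) + 0.15 × d(4+) = -0.23. All four patterns below satisfy it, and each implies a CACE of -0.23 / 0.225 = -1.02 SD per full attendance.

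| Pattern | d(1-3) | d(4+) | Simulated median CACE | One-sided rejection, ITT / CACE |
|---|---|---|---|---|
| Linear per round | -0.34 | -0.85 | -1.03 | 0.824 / 0.836 |
| Only 4+ helps | 0 | -1.53 | -1.03 | 0.769 / 0.785 |
| Any attendance helps | -0.51 | -0.51 | -1.02 | 0.824 / 0.829 |
| Only 1-3 helps | -0.77 | 0 | -1.02 | 0.844 / 0.842 |

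(1,500 trials per row, robust standard errors.) A separate simulation with other assumptions (ITT -0.2 SD, 40% attending) gave -0.86 for 4+ only, -0.87 for 1-3 only and -0.85 for linear. There the CACE and the primary agreed on significance in 98-100% of runs.

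**Step 3: the exposure does not match the threshold.** Phase one offers at least six rounds and phase two at least four. Four rounds attended is 4/6 = 0.67 in one setting and 4/4 = 1.0 in the other, so a regular attender has no fixed value on the model's scale.

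**Step 4: incomplete recording.** Let q be the share of attendances recorded and linked among T2 respondents, the only people in the model. Let c be control attendance as a fraction of intervention attendance. If missing attendance is set to zero,

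inflation factor = (1 - c) / (q_int - c × q_ctl).

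With equal recording in both arms this is 1/q:

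| q (assumed) | 1/q | Simulated |
|---|---|---|
| 90% | 1.11 | 1.12 |
| 80% | 1.25 | 1.25 |
| 70% | 1.43 | 1.41 |
| 50% | 2.00 | 1.99 |

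The direction is not fixed. With 80% recorded in the intervention arm and none in controls, c = 20% gives 0.8/0.8 = 1.00 and c = 30% gives 0.7/0.8 = 0.875 (simulated 1.00 and 0.88).

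**Step 5: cost.** Attendance hours taken from forms equal the returned share times the true hours. A 70% return would understate them by 30%. A returned form that cannot be linked still counts as time, so the cost bias and the CACE bias need not be equal.

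**The case against.** The CACE is a legitimate estimand, the primary estimate is untouched, and the mismatch concerns one secondary hypothesis. All of that stands. A reader might infer that the plan will declare (c) supported whenever the primary is significant. The protocol sets no such rule and nowhere calls the CACE independent evidence. What remains is that it offers no other quantitative analysis for (c). The Exploratory Analysis section lists no comparison by frequency of attendance, and its item on attendance concerns face-to-face versus virtual mode only.

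A reader might also infer that the forms simply inflate the estimate in the intervention's favour. The documents do not support that, for four reasons:

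- No completion rate is given. The Ethics & Participation section has forms handed out on arrival, a reminder at the end, and consent sought through the form.
- Staff who decline forms may also skip the voluntary T2 survey, so capture among those analysed could be higher than capture overall.
- The handling of unlinked forms is not stated and may properly be left to an SAP. The link is a plausible weak point, because the surveys accept a work email as an alternative identifier while the form is described as using initials and birth day and month.
- Under-recording rescales the estimate. It does not turn a null ITT result into a significant one, and it would magnify a harmful effect as much as a helpful one.

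**Conclusion.** The main point holds from the protocol's text alone: the model written for (c) is the primary estimate divided by a first-stage difference, and it cannot compare regular with less regular attendance. Its near-identical answers to opposite patterns (-1.03 and -1.02 SD) follow from the algebra. Only their level depends on the assumed attendance distribution and the -0.23 SD effect.

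The recording point is conditional. To the extent that intervention-arm attendance is under-recorded and counted as zero, the CACE is inflated by about 1/q. The range of 1.1 to 2.0 rests on an assumed q of 90% to 50%, and much poorer recording in controls can cancel or reverse it. Its actual size is unknown.

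**What to change.** 1. Describe the CACE as the complier effect of attendance under a linear dose assumption, and state that it rescales the primary estimate and is not separate evidence on regularity.
2. Address the contrast in (c) by comparing 4+, 1-3 and no rounds within the intervention arm, adjusted for baseline GHQ-12 and X, and label it observational.
3. Compare the number of returned forms with the headcounts already requested from each local authority, and report a sensitivity range for the CACE and for staff-time cost. Do not scale individual attendance by headcount. Headcounts are described without a split by arm and may include controls, T2 non-respondents and facilitators. Setting linked forms alone against headcount would overcorrect, given the 50% to 75% loss to follow-up that the sample size table allows for. Comparing all forms with headcount does not reveal linkage failure.
4. If it is not already there (the questionnaire is not shown), add an item on the number of rounds attended to the phase two T2 survey, due in March and April 2021. It checks that phase only, since phase one data collection is complete.

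The cost is wording, one descriptive analysis, one sensitivity analysis and one survey item. Hypothesis (c) can then claim less, and the within-arm comparison is open to confounding, because staff who attend often may differ from those who do not.
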